## 2.5.2 Statistical Analysis

Change of each outcome from baseline will be presented by median (IQR). Primary analysis will be performed by paired t-test comparing continuous outcome in 12-weeks vs. baseline. All data will be tested for normality, and non-normal data will be tested by Wilcoxon signed rank test. We will also use mixed effect models with restricted maximum likelihood estimation to test the change of outcome during the 12 weeks of intervention.

Demographics and baseline characteristics will be listed and summarized descriptively. Safety will be evaluated via the incidence of AE's, changes in clinical labs, and vital signs. AEs will be coded by system organ class and preferred term according to the most recent edition CTCAE. AEs will be summarized by frequency, severity, and relationship to study medication. Clinical labs will be compared to normal ranges and flagged if found to be of clinical concern. Results will be presented as observed changes and depicting changes from baseline to defined study timepoints.

## 2.5.3 Pharmacokinetics Analyses

Plasma concentration-time data of CXA-10 parent and metabolite(s) will be displayed in tables and/or graphs. Individual plasma concentration-time data will be pooled, and population pharmacokinetics will be performed using a currently acceptable method as permitted by the data. Population PK parameters such as Clearance (CL) and volume of distribution (V) will be determined, as the data allow. In addition, the influence of various covariates (e.g. BMI) of the PK parameters will be examined.

## 2.5.4 Pharmacodynamics Analyses

### 2.5.4.1 Biomarker Analyses

PD endpoints will be listed and summarized descriptively by assessment time. Change from baseline in lipid profile (e.g. total cholesterol and triglycerides) will be separately analyzed using an appropriate model. Additional biomarkers (e.g. leptin, MCP-1, IL-6, etc.) may also be analyzed as appropriate. Relevant covariates (e.g. underlying disease) will be included. The

least square mean difference and associated 95% confidence intervals for each assessment time and across all assessment times will be obtained from the model.

#### **2.5.4.2 Pharmacokinetic/Pharmacodynamic Analyses**

PK/PD modeling will be conducted to better define exposure-response and dose determination for future studies, as appropriate.

#### **2.5.5 Handling Missing Data**

Every effort will be made to minimize the missing data in the study. We will record reasons for drop-out and compare baseline characteristics between participants who do and do not complete the study. A mixed effect model approach will be used to take into account missing data for the endpoints which are measured at more than just baseline (or screening) and Week 12. In the event of missing data, a complete-case analysis will be performed as a sensitivity analysis to assess the robustness of the treatment effect. In the event Week 12 data is missing for endpoints routinely collected only prior to the start of treatment and at Week 12, a mixed model approach will not be applicable. Accordingly, methods for assessing the impact of missing data on conclusions will be a function of several factors. These factors include: the extent of missing data at Week 12, the reasons data may be missing for individual subjects, and whether or not any post-baseline are available, prior to Week 12 (e.g., at early discontinuation). We will also use multiple imputation approach to impute these values to perform a sensitivity analysis.

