## 2.5 STATISTICAL ANALYSIS

### 2.5.1 Sample Size Determination

We plan to enroll 30 subjects with PAH, allowing for a conservative drop-out rate of 10%, in this open label trial of oral CXA-10. We expect to see decrease in the PVR after 12 weeks of therapy. The intention to treat (ITT) population will consist of all subjects who have received at least one dose of study medication. To estimate our effect size for power calculations, we use data from the SUPER-1 sildenafil PAH trial (a randomized placebo control trial evaluating the effects of 20 mg, 40 mg or 80 mg TID of sildenafil in subjects with PH). Using the hemodynamic data from the 80 mg arm of the SUPER-1 trial and making a conservative assumption that our therapy will only have an effect that is 70% of sildenafil (decrease in PVR of 2.3 woods units with SD of 4.1), the sample size required for 80% power and P = 0.05 is 27 subjects (Table 2). We anticipate more than sufficient power to detect vasodilatory effects of NO2-OA administration (decreased PVR) after 3 months of therapy. Based on our extensive phase 1 data with CXA-10 formulations, we

anticipate the drug will cause no systemic blood pressure changes and no increases in methemoglobin levels.

**Table 2 Required sample size for different effect,  
Power =0.8 ,  $\alpha=0.05$ , two sided test**

% of Sildenafil	Mean (SD) PVR change, Woods unit	N
90	3.0 (4.9)	23
80	2.6 (4.2)	23
70	2.3 (4.1)	27

With safety as the primary outcome measure, we use Fleming's single stage phase II design with the following assumptions:  $\alpha = 0.05$ , Power= 0.80, lower proportion for rejection 70% (with no SAEs), higher proportion of acceptance 90% (with no SAEs) with maximum recruited patients of 27 patients resulting in a minimum number of success (with no SAEs to indicate that the treatment is safe) is 24. Thirty patients will be enrolled to compensate for up to 10% lost-to follow-up.

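### Sections 2.5.2 and 2.5.5 give the completer-only paired test and the mixed model opposite roles, and 2.5.5 wrongly rules out a mixed model for PVR and other two-visit endpoints

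*Combined protocol and SAP*

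**What the plan says.** Section 2.5.2: "Primary analysis will be performed by paired t-test comparing continuous outcome in 12-weeks vs. baseline". A Wilcoxon signed rank test replaces it for non-normal data, and REML mixed models are added as a further analysis.

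Section 2.5.5 divides the endpoints by visit schedule:

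- **Measured at more than baseline and Week 12.** A mixed model takes account of missing data. Then: "In the event of missing data, a complete-case analysis will be performed as a sensitivity analysis to assess the robustness of the treatment effect".
- **Measured only before treatment and at Week 12.** If Week 12 is missing, "a mixed model approach will not be applicable". The approach is left to depend on how much is missing, why, and whether any earlier post-baseline value exists. Multiple imputation is added as a sensitivity analysis.

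Section 2.5.1 allows for 10% drop-out and defines the population: "The intention to treat (ITT) population will consist of all subjects who have received at least one dose of study medication".

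By section 2.2.2 and Appendix A, 6MWD, NT-proBNP and PAH-SYMPACT are also measured at Weeks 4 and 8. RHC and echocardiography are done only before treatment and at its end. Under section 6.4.8, subjects who stop before Week 10 are asked for the end-of-treatment assessments without the RHC.

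**The concern.** A paired test needs both values, so it is a complete-case analysis even though 2.5.2 does not call it one. Section 2.5.2 ranks it first, while 2.5.5 ranks complete-case analysis as a sensitivity check behind the mixed model. Once a Week 12 value is missing, the two can give different answers for 6MWD, NT-proBNP and PAH-SYMPACT, and nothing says which is reported as the result.

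For PVR, the primary efficacy endpoint, 2.5.5 sets the mixed model aside on an incorrect ground. No main method is then named for the all-dosed population, which a completer-only test cannot represent. Missing PVR is also tied to stopping treatment, because stops before Week 10 have no end-of-treatment RHC. In a one-arm trial the change from baseline is the whole efficacy result, so the analysis set matters.

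**Working it through.** **1. The plan's own sample size.** Inputs from section 2.5.1: "decrease in PVR of 2.3 woods units with SD of 4.1", two-sided 0.05, 80% power. For a paired t-test the noncentrality is (2.3/4.1) × √n. At n = 27 this is 0.561 × 5.196 = 2.91 on 26 df, giving power 0.801; n = 26 gives 0.785. The stated 27 reproduces, and 27/0.9 = 30. The calculation thus assumes a paired test in 27 completers.

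**2. Roles side by side.**

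| Analysis, repeated endpoints | 2.5.2 | 2.5.5 |
|---|---|---|
| Paired t-test (completers) | primary | sensitivity |
| Mixed model | additional | method for missing data |

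**3. Is a two-visit mixed model possible?** Keep baseline and Week 12 both as responses, with an unstructured covariance. When only Week 12 can be missing, the likelihood estimate of the change is

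ȳ12(completers) + b × [ȳ0(all) − ȳ0(completers)] − ȳ0(all),

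where b is the completers' regression slope of Week 12 on baseline. Subtracting this from the completer mean change leaves (1 − b) × [ȳ0(all) − ȳ0(completers)]. That is zero when nobody is missing, so the model then returns the paired result.

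A fitted example, in random-intercept form: 30 simulated subjects with the three highest baselines missing Week 12, hence 57 observations. REML converged.

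| Analysis | Change, WU | SE |
|---|---|---|
| Mixed model, all 30 | −1.64 | 0.73 |
| Paired test, 27 completers | −1.33 | 0.72 |
| Mixed model, 27 completers | −1.33 | 0.72 |
| Mean before deletion | −1.64 | |

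This one data set shows feasibility, not a general size of effect.

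**4. Size for PVR.** Simulation of 30 subjects with 10% missing and true change −2.3 (SD 4.1). Assumed, because the documents do not give them: baseline SD 5 WU, baseline–change correlation 0 to −0.6, drop-out log-odds of 1 per SD. Positive bias is against the drug.

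| Drop-out depends on | Completers, WU | Mixed model, WU |
|---|---|---|
| nothing (MCAR) | about 0 | about 0 |
| baseline | 0.00 to +0.22 | 0.00 |
| the unseen change | −0.37 to −0.38 | −0.24 to −0.37 |

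A second set-up (SD 4.5 WU at both visits, between-visit correlation 0.5 to 0.8, no drug effect, three missing among high-baseline subjects) gives completers +0.11 to +0.27 WU and the likelihood estimate about 0.

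As a plain bound, let 27 completers change by −2.3 and the three missing subjects by x. The all-dosed mean is (27 × −2.3 + 3x)/30. For x = −2.3, 0, +2.3 and +4.1 it is −2.30, −2.07, −1.84 and −1.66, so the completer mean overstates the fall by 0, 0.23, 0.46 or 0.64 WU.

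**5. Size for 6MWD.** No drug effect, 30 dosed. Assumed: subject SD 90 m, SD of 12-week slopes 40 m, visit noise 25 m; subjects missing Week 12 are drawn from the worst Week 8 changes.

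| Missing | Completers, no final value | With early-termination value (assumed Week 9) |
|---|---|---|
| 3 | +4.4 m | +0.6 m |
| 5 | +8.2 m | +1.1 m |

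The likelihood estimate is near 0 in both rows. The standard error of the mean change is about 10 m.

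**The case against.** - **The conflict is partly inference.** Section 2.5.5 never calls the mixed model primary, and 2.5.2 adds it only as a further analysis. True, but calling complete-case analysis a sensitivity check implies that something else is the main analysis.
- **The two-visit statement can be defended.** Endpoints are defined as change from baseline. With change as the response, a subject with only a baseline contributes nothing. This stands for that parametrisation, but 2.5.5 does not specify it, and the alternative is standard.
- **Multiple imputation is already planned** for two-visit endpoints. Under missing at random, imputing from baseline targets the same quantity as the likelihood model, so for PVR the change is largely one of rank. It is still worth making, because no main method for all dosed subjects is named.
- **Early stoppers are asked for final non-RHC assessments.** This sharply reduces possible 6MWD bias. However, the plan does not say whether those values enter the Week 12 analysis.
- **The affected endpoints are secondary.** The primary endpoint is adverse-event incidence. This limits the seriousness.

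A reader might infer that drop-outs will bias the Week 12 changes, and towards benefit. The documents do not support that. They give no drop-out mechanism; bias is zero under MCAR; and high-baseline drop-out moves PVR against the drug. Nor would a mixed model cure everything: when drop-out depends on the unseen change, most of the bias remains.

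**Conclusion.** The concern holds in a limited form. For the repeated continuous endpoints the two sections rank the same analyses in opposite order, and the statement that a mixed model cannot be used with two visits is incorrect when baseline is a response. Both are faults of the text and need no assumption.

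The numerical consequence does rest on assumptions. With selective drop-out on observed values, completer bias is about +4 to +8 m for 6MWD if early stoppers give no final value, about +1 m if those values are obtained and used, and about +0.1 to +0.3 WU for PVR, against the drug, if high-baseline subjects leave. The 6MWD figures are below the standard error of about 10 m. The required 27 completers and 30 enrolled do not change. This should be corrected before analysis, but it does not undermine the trial.

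**What to change.** In both 2.5.2 and 2.5.5:

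1. Name one primary estimator for continuous endpoints in all dosed subjects: a REML mixed model with baseline and on-treatment visits through Week 12 as responses, categorical visit, unstructured covariance, Kenward–Roger degrees of freedom, and the Week 12 minus baseline contrast. Exclude Week 16. Baseline and Weeks 4, 8 and 12 need 4 × 5/2 = 10 covariance parameters, so pre-state a simpler fallback structure.
2. Use the two-visit form for PVR and the other RHC and echocardiographic endpoints, and delete the sentence saying it is not applicable.
3. State which pre-dose value is baseline where there are two (6MWD is scheduled at Visits 1 and 3), and how early-termination values are used.
4. Make the paired t-test, or Wilcoxon test, the complete-case sensitivity analysis.
5. Keep multiple imputation and add a delta-adjusted version for drop-out related to the unseen change.

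The cost is wording and slightly more analysis work, with no new data or subjects. The downside is reliance on model assumptions in a small sample.

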#### **2.5.6 Data Management**

The study forms will be paper-based in that the data will be first recorded on paper forms at the time of the study visits. A relational database will be constructed on a local server with daily backups where only select research team members will have access to the database. The database will include data entry forms with the same appearance as the paper forms to facilitate accurate data entry and routine data edit checks for consistency both within and between forms. After data entry, the paper forms will be archived in secure file cabinets. All study subjects will be assigned unique study identifiers that will appear on all data collection instruments, documents, and files used in the statistical analysis and manuscript preparation. The case report forms with study IDs will be housed in the same chart as personal identifier documents are while the subject is active in the protocol. Only limited team members will have access to charts and database. No personal information concerning study participants will be released without their written consent. Other data quality assurance measures will include verifying the data, out of range data checks, and repeated evaluation of the data process. A separate data management document including variable characteristics, codebooks, validation role for each variable, characteristics of database file will be created and archived with original data.

### **3. HUMAN SUBJECTS**

The proposed study population will consist of 27 subjects with PAH. In order to achieve this number, it is anticipated that approximately 30 participants may need to be enrolled into this study to account for subjects who may not qualify the eligibility criteria or are withdrawn for any reasons.

#### **3.1 SUBJECT POPULATION**

##### **3.1.1 Inclusion of Women and Minorities**

Women and individuals from minority groups who meet the inclusion criteria and have none of the exclusion criteria, will be enrolled without restriction as dictated by the study protocols. Every effort will be made to enroll participants in this research in a distribution, which mirrors the study population of the Pittsburgh area.

### **3.1.2 Inclusion of Children**

This investigation will not enroll children based upon lack of safety data in children with regards to the investigational product.

### **3.1.3 Inclusion of Prisoners**

This investigation will not enroll prisoners.

## **3.2 INCLUSION CRITERIA**

The following criteria will be required on ALL subjects:

- Male or female between 18-80 years of age inclusive at Screening
- Weight  $\geq$  40 kg or 88 lbs
- Have a WHO Classification of Functional Status Class II or III
- Must meet all of the following hemodynamic criteria by means of a right heart catheterization: mPAP of  $\geq$ 25 mmHg, PVR  $\geq$  3 wood units, PAWP of  $\leq$ 15 mmHg. A clinical RHC done within 2 months is acceptable to determine eligibility
- Meet all of the following pulmonary function test parameters, completed no more than 12 months before Screening or at screening: forced expiratory volume in one second (FEV1)  $\geq$  60% of predicted normal and forced vital capacity (FVC)  $\geq$  60%
- A 6 MWD test of  $\geq$  100 m and  $\leq$  600 m at Screening
- Participants enrolled in an exercise program for pulmonary rehabilitation must be in a stable program 1 month prior to Screening and must agree to maintain their current level of rehabilitation throughout the study. If subjects are not enrolled in an exercise training program for pulmonary rehabilitation they cannot enroll during the Screening/Baseline Period or throughout the study
- If receiving 3-hydroxy-3-methyl-glutaryl-coenzyme A (HMG-CoA) reductase inhibitors (i.e., statins) subjects must not have changed their dose  $<$ 4 weeks prior to Screening
- If receiving simvastatin-containing products: simvastatin (Zocor), Vytorin, or any other combination therapy containing simvastatin, the subject's simvastatin dose should not exceed 20 mg/day  
Note: Subjects using a simvastatin product at dose  $>$  20 mg/day may be rescreened if their dose has been adjusted to  $\leq$  20 mg/day, at least 4 weeks prior to Screening with no dose or regimen changes within 4 weeks prior to Baseline
- Subjects must be receiving one or more of the following previously approved PAH therapies: phosphodiesterase type 5 inhibitors (PDE5), endothelin receptor antagonist (ERA), soluble guanylate cyclase (sGC) stimulator, prostanooids, prostacyclin receptor agonists and must be on stable doses ( $\geq$  3 months) with no dose adjustment within 1 month of Screening
- Ability to provide written informed consent

### 3.3 EXCLUSION CRITERIA

Subjects meeting any of the following exclusion criteria at baseline will be excluded from participating in study:

- Portopulmonary hypertension and pulmonary veno-occlusive diseases
- Congenital heart defects (i.e., atrial septal defects, ventricular septal defects, and patent ductus arteriosus) repaired less than 1 year prior to Screening (Group 1 classification of Pulmonary Hypertension)
- Systolic blood pressure > 160 or < 90 mmHg or diastolic blood pressure > 110 mmHg at Screening
- An average QTcF on supine triplicate ECGs at Screening (Visit 1) of >500 msec Acute myocardial infarction or acute coronary syndrome (ST-Elevation Myocardial Infarction (STEMI), Non STEMI (NSTEMI) and/or unstable angina) within the last 90 days prior to Screening
- Recent cerebrovascular accident/transient ischemic attack (CVA/TIA) within the last 90 days prior to Screening
- Recent hospitalization for left heart failure within the last 90 days prior to Screening
- Clinically significant aortic or mitral valve disease defined as greater than moderate regurgitation or moderate stenosis; pericardial constriction; restrictive or constrictive cardiomyopathy; left ventricular dysfunction (LVEF < 50%); left ventricular outflow obstruction; symptomatic coronary artery disease; autonomic hypotension; or fluid depletion in the opinion of the investigator
- Evidence of a life-threatening cardiac arrhythmias on ECG at Screening as determined by the physician investigator
- Personal or family history of congenital prolonged QTc syndrome or sudden unexpected death due to a cardiac reason
- Receiving intravenous inotropes (e.g. dopamine, dobutamine) within 2 weeks prior to Screening
- History of angina pectoris or other condition that was treated with long or short acting nitrates <12 weeks of Screening
- The subject has a history of herbal or natural medication use (including fish oil) within 2 weeks or 5 half-lives, whichever is longer, prior to Baseline
- Subject has taken prednisone at doses > 15 mg/day; if immunosuppressive medications are used the dose must be stable within 12 weeks prior to Screening and throughout the study
- The subject is currently taking a drug that may affect the assay measurement of serum creatinine (e.g. cimetidine, Bactrim, Pyridium)
- Newly prescribed drug or increased dose of an existing drug that is known to prolong the QTc interval and has been associated with Torsades de Pointes
  - Note: Stable doses of these drugs are permitted (i.e., subject has received the same dose and regimen for at least 30 days prior to Screening with no anticipated changes to the dose or regimen during the course of the study)
- The subject is currently taking dimethyl fumarate (Tecfidera™)

- Females with a positive urine pregnancy test at Screening or prior to dosing or who are pregnant or breastfeeding or who are trying to conceive
- Recent (within 6 months) history of abusing alcohol or illicit drugs
- History of any primary malignancy, including a history of melanoma or suspicious undiagnosed skin lesions, with the exception of basal cell or squamous cell carcinomas of the skin or cervical carcinoma in situ or other malignancies curatively treated and with no evidence of disease for at least 5 years or prostate cancer who is not currently or expected, during the study, to undergo radiation therapy, chemotherapy, and/or surgical intervention, or to initiate hormonal treatment
- Cardiovascular, liver, renal, hematologic, gastrointestinal, immunologic, endocrine, metabolic, central nervous system or psychiatric disease that, in the opinion of the investigator, may adversely affect the safety of the subject and/or efficacy of the investigational product or severely limit the lifespan of the subject other than the condition being studied
- Clinically significant hyperthyroidism or hypothyroidism not adequately treated
- Any other condition and/or situation that causes the Investigator to deem a subject unsuitable for the study (e.g., due to expected study medication non-compliance, inability to medically tolerate the study procedures, or a subject's unwillingness to comply with study-related procedures)
- The subject has known hypersensitivity to the CXA-10, the metabolites, or formulation excipients
- The subject has had treatment with any investigational drug within 30 days or 5 half-lives (whichever is longer) prior to Screening or plans to participate in an investigational drug study at any time during this study

Subjects who fail inclusion/exclusion criteria may be re-screened once.

Herbals, natural medications and fish oil	These agents typically are of unknown composition and quality, so this exclusion is included in most clinical trial protocols.	If the subjects are taking herbals, natural medications and fish oil, the subject should stop taking CXA-10 because there are typical risks of agents.

		If there is an AE, the study team will not know if it is due to CXA-10 or this herbals, natural medications and fish oil. It is known that OTC products contain unexpected materials and/or have unexpected effects on prescribed drugs.
Drugs that may affect the measurement of serum creatinine (e.g. cimetidine, Bactrim, Pyridium).	The study team will monitor the subject's renal function (a safety endpoint), so agents that affect the measure will confuse the interpretation of the safety signal.	Often there are other therapeutic options which do not impact measurement of sCr. Also, if the acute therapy and labs are not checked during the period of therapy, then it may not be a problem.
Dimethyl fumarate (Tecfidera™)	CXA-10 "like" drug which is an Nrf2 activator, so use will confuse interpretation of study results.	Stop CXA-10 if the patient needs DMF.
Simvastatin at doses greater than 20 mg (Zocor), Vytorin, or any other combination therapy containing simvastatin at doses greater than 20 mg.	Drug-drug interaction study demonstrated that CXA-10 could raise simvastatin acid level probably due to an effect on a transporter.	Use alternate statin, since this interaction only is for simvastatin. This is not a general statin interaction.
Any other investigational drug regardless of route (topical, intranasal, etc).	The study team will not allow 2 investigational agents (which are not designed to be co-administered) be co-administered. The study team will not know if CXA-10 drug or other investigational agent taken by patient caused an AE since there is not enough	The subject can only participate in one clinical study at a time.

	known about how CXA-10 interacts with other investigational agents.	
--	---	--

